- The investigator believes that for safety reasons (eg, AE) it is in the best interest of the subject to discontinue study treatment

All attempts to obtain imaging studies at the time of treatment discontinuation or EOT Visit should be made to assess for radiographic progression. Study drug will be continued for subjects who have increasing PSA values in the absence of radiographic or clinical progression. Although serial PSA measurements will be performed in this study, progression or change in PSA values should not be used as the lone indicator for disease progression or treatment discontinuation. If a

subject discontinues study drug, but does not withdraw consent for follow-up, scheduled assessments should continue according to the Follow-up Phase in the Time and Events Schedule.

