11.7. Safety Analyses

The safety parameters to be evaluated are the incidence, intensity, and type of AEs, vital signs (blood pressure), ECG, and clinical laboratory results. Exposure to study drug and reasons for discontinuation of study treatment will be tabulated.

Adverse Events

The verbatim terms used in the eCRF by investigators to identify AEs will be coded using the most current Medical Dictionary for Regulatory Activities (MedDRA) and will be graded according to NCI-CTCAE (Version 4.03). Treatment-emergent AEs are AEs that occur or worsen on or after first dose of study drug through 30 days after the last dose of study drug and will be included in the analysis. Adverse events will be summarized by system organ class and preferred term, and will be presented overall and by treatment group. Serious adverse events and deaths will be provided in a listing. All AEs resulting in discontinuation, dose modification, dosing interruption, or treatment delay of study drug will also be listed and tabulated by preferred term.

Clinical Laboratory Tests

Clinical laboratory test results will be collected from Screening and through 30 days after last dose of study drug. Laboratory data will be summarized by type of laboratory test. Parameters with predefined NCI-CTCAE (Version 4.03) toxicity grades will be summarized. Change from baseline to the worst AE grade experienced by the subject during the study will be provided as shift tables.

Electrocardiogram (ECG)

Electrocardiogram data obtained at screening will be summarized by ECG parameter.

Vital Signs

Descriptive statistics of blood pressure (systolic and diastolic) values and changes from baseline will be summarized at each scheduled time point. The percentage of subjects with values beyond clinically important limits will be summarized.

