### **1.2. Study Design**

This is a randomized, double-blind, placebo-controlled, multinational, multicenter Phase 3 study to determine if subjects with mHSPC will benefit from the addition of apalutamide to ADT. Enrollment of approximately 1,000 subjects is planned for this study. Subjects who meet all of the inclusion criteria and none of the exclusion criteria will be stratified by Gleason score at diagnosis, prior docetaxel use, and geographic region, and then randomly assigned in a 1:1 ratio to the apalutamide plus ADT or matching placebo plus ADT group.

The study will include a Screening Phase of up to 28 days before randomization to establish study eligibility. Subjects will receive treatment in 28-day treatment cycles during the Treatment Phase until

disease progression or the occurrence of unacceptable treatment-related toxicity. Subjects must discontinue study drug with documented clinical progression. After discontinuation of study drug, subjects will have an End-of-Treatment Visit within 30 days after the last dose of study drug. In the event of a positive study result at either of the interim analyses or at the final analysis, all subjects in the Treatment Phase will have the opportunity to enroll in an Open-label Extension Phase, which will allow subjects to receive active drug (apalutamide) for up to 3 years.

Subjects will be monitored for safety starting from the signing of informed consent until 30 days after the last dose of study drug. Adverse events including laboratory AEs will be graded and summarized using the National Cancer Institute Common Terminology Criteria for Adverse Events (NCI-CTCAE) Version 4.03. Dose modifications will be made as required according to dose modification rules. An Independent Data Monitoring Committee (IDMC) will be commissioned for the study to provide recommendation during the planned interim efficacy analysis and regular safety review.

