### 4.2. Disposition Information

Subject enrollment and disposition will be summarized by treatment group. The summary of subject disposition will display the number of subjects randomized, and the numbers of subjects in ITT, safety. The summary will also include the number and percent of subjects who completed the study and who

discontinued from the study and study treatment, respectively, and reason for discontinuation as documented in the subject status case report form.

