- Overall summary of AEs: the number and percentage of subjects who experienced any AE, any serious adverse event (SAE), any treatment-related AE, any treatment-related SAE, any discontinuations due to an AE, and any deaths
- All AEs by SOC and preferred term All AEs by SOC, preferred term, and toxicity grade
- Grades 3 or 4 AEs by SOC and preferred term
- Treatment-related AEs by SOC and preferred term
- Treatment-related AEs by SOC, preferred term, and toxicity grade
- Treatment-related Grades 3 or 4 AEs by SOC and preferred term
- AEs that led to study drug discontinuation by SOC and preferred term. Study drug discontinuation will be determined from the treatment disposition CRF (where reason for discontinuation is “Adverse Event”) and the specific AE will be determined from the AE CRF page (where action taken is “Drug withdrawn”)
- AEs that led to study drug discontinuation by SOC, preferred term, and toxicity grade
- AEs that led to dose modification by SOC, preferred term, and toxicity grade
- All SAEs by SOC and preferred term
- All SAEs by SOC, preferred term, and toxicity grade
- Deaths will be summarized by time period (on-study vs. during follow-up) and cause of death.

Subject listings of all AEs by toxicity grade, Grades 3 or 4 AEs, all SAEs, AEs that led to study drug discontinuation, dose modification, and all deaths will be provided as well.

Narratives will be written for the following subjects in the final clinical study report:

- Subjects who die  $\leq 30$  days after the last dose of study drug
- Subjects who discontinue study drug due to treatment-emergent AE
- Subjects who experience a treatment-emergent SAE
- Subjects who experience seizure
- Subjects who experience Grade 3 or higher treatment-emergent major adverse cardiovascular events (MACE) including ischemic heart disease, cardiac failure, cerebrovascular disease, and arrhythmias
- Subjects who experience treatment-emergent primary cancers

Subjects who experience other Grade 3 or higher treatment-emergent adverse events of special interest.

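### SAP 6.1 leaves an AE marked 'Drug withdrawn' out of the discontinuation tables when the disposition page gives a reason other than 'Adverse Event'

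*SAP*

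**What the plan says.** SAP 6.1 attaches a derivation rule to the table, by SOC and preferred term, of AEs that led to study drug discontinuation. The first half reads: "Study drug discontinuation will be determined from the treatment disposition CRF", with the condition in brackets that the reason given there is 'Adverse Event'. The second half, joined by 'and', reads: "the specific AE will be determined from the AE CRF page (where action taken is “Drug withdrawn". The next table in the list repeats the topic by toxicity grade without a rule of its own, so the same rule presumably applies.

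Three other outputs in SAP 6.1 cover the same topic, and none has a stated source: a line in the overall AE summary for any discontinuation due to an AE, a subject listing, and narratives for "Subjects who discontinue study drug due to treatment-emergent AE". The neighbouring table of AEs leading to dose modification has no disposition condition.

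Protocol 11.7 describes the output without a disposition condition: "All AEs resulting in discontinuation, dose modification, dosing interruption, or treatment delay of study drug will also be listed and tabulated by preferred term".

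SAP 4.2 summarises subjects who "discontinued from the study and study treatment, respectively, and reason for discontinuation as documented in the subject status case report form". That form has a different name from the one in SAP 6.1, and the SAP does not say whether the two are the same.

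**The concern.** The disposition page records why treatment stopped. The action-taken field on the AE page records, event by event, what the investigator did about that event. SAP 6.1 lets the first act as a filter on the second. If the pages disagree, an event that the investigator linked to stopping the drug does not reach the table meant to show such events. The SAP has no rule for disagreement in either direction, and no table based on the AE page alone.

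Disagreement is plausible in this trial because several reasons to stop can apply to one man at once. Protocol 10.2 lists clinical progression, repeated dose reductions for treatment-related toxicity, seizure or Grade 4 neurotoxicity, and unblinding. Beside these it has a general safety item: "The investigator believes that for safety reasons (eg, AE) it is in the best interest of the subject to discontinue study treatment". Under Protocol 12.3.2, progression itself is not recorded as an AE or SAE term, but its clinical sequelae are reported when they meet the SAE definition. A man can therefore have both a recorded event and progression as his reason for stopping.

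At stake is a standard tolerability display: which events led men to stop apalutamide, and how often compared with placebo. The efficacy analyses are not affected.

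**Working it through.** The documents give no expected rate of AE discontinuation and no rate of disagreement between the pages, so there is no figure of the plan's to reproduce. The check is of the rule itself, followed by an illustration on assumed shares.

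**Step 1: sort the men in one arm by the two pages.**

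| Disposition reason | AE marked 'Drug withdrawn' | Men | In the SAP 6.1 SOC/preferred-term table? |
|---|---|---|---|
| 'Adverse Event' | Yes | a | Yes |
| Another reason | Yes | b | No |
| 'Adverse Event' | No | c | No event to show |
| Another reason | No | d | No, correctly |

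**Step 2: compare the possible counts.**

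- SAP 6.1 tables by SOC/preferred term: a
- AE page alone: a + b
- Disposition page alone: a + c

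The SAP table minus the AE-page count is a − (a + b) = −b, so for these tables the rule can only keep or reduce the number of men shown. The disposition-page count minus the AE-page count is (a + c) − (a + b) = c − b, which can have either sign.

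**Step 3: set this beside the protocol.** Protocol 11.7 covers all AEs resulting in discontinuation. If the action-taken field is the investigator's statement that an event resulted in withdrawal, the protocol's set is a + b and the SAP delivers a. The two agree only when b = 0.

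**Step 4: illustrate the size.** "Enrollment of approximately 1,000 subjects is planned for this study", randomised 1:1, so n = 1,000 / 2 = 500 per arm. Let p be the share of men with an AE marked 'Drug withdrawn', so a + b = n × p. Let m be the share of those men with another disposition reason. Then a = n × p × (1 − m). Both p and m are assumptions, and fractions of a man are expected values.

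| p | a + b | a at m = 10% | a at m = 20% | a at m = 30% |
|---|---|---|---|---|
| 5% | 25 | 22.5 (4.5%) | 20 (4.0%) | 17.5 (3.5%) |
| 8% | 40 | 36 (7.2%) | 32 (6.4%) | 28 (5.6%) |
| 10% | 50 | 45 (9.0%) | 40 (8.0%) | 35 (7.0%) |

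At m = 0 nothing is lost.

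**Step 5: consider the arms.** If p were 10% in both arms but m were 10% in one and 30% in the other, the tables would show 9.0% against 7.0%. That is a gap of 2.0 percentage points produced by discordance alone. Exchanging the arms reverses its sign. The documents do not say which arm would have the larger m.

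**The case against.** Four counter-arguments deserve weight.

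- **The protocol wording is causal and names no data source.** Protocol 11 leaves specific details to the SAP. Taking the investigator's recorded reason for stopping is a legitimate way to define what resulted in discontinuation; if that reason is progression, one can argue that the AE was not the cause. This stands as an argument about definition. It does not explain why the investigator's own 'Drug withdrawn' entry should be set aside without comment.
- **Counting on the AE page has its own bias.** Sequelae of progression that are reported as SAEs could be marked 'Drug withdrawn' and so bring disease-driven stops into a tolerability table. This stands, and is why the disposition reason should be displayed.
- **Data cleaning may remove the mismatches.** Protocol 17.5 provides for queries, including automatic ones, and Protocol 17.6 for resolving discrepancies with the investigator. Neither names this cross-page check, and the CRF is not in the documents. Mismatches may be fewer as a result, but nothing shows that they are removed.
- **No event disappears.** The events stay in the all-AE tables and, where they qualify, in the Grade 3 or 4, treatment-related and SAE tables. Every treatment-emergent SAE, and every death within 30 days of the last dose, also gets a narrative. This stands and limits the consequence to the discontinuation outputs.

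A reader might infer more: that the rule can only lower the headline rate of discontinuation due to AEs. The documents do not support this. The rule is attached to the SOC/preferred-term table, and the overall-summary line has no stated derivation. If that line uses the disposition page, its count is a + c, which can lie above or below the AE-page count.

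A reader might also infer a bias in favour of apalutamide. That is not supported either. SAP 1.4 assumes a median rPFS of 20 months on control and 30 months on apalutamide, so competing progression could be more frequent on placebo. The undercount would then fall more on placebo and make apalutamide look relatively worse. Other competing reasons could act the other way.

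**Conclusion.** The point holds as a gap in safety reporting. On the natural reading of SAP 6.1, the SOC/preferred-term and by-grade tables omit a treatment-emergent AE marked 'Drug withdrawn' when the disposition page gives another reason, which is narrower than Protocol 11.7. The rule also leaves a man with reason 'Adverse Event' but no event so marked without an entry in those tables.

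The size and the direction by arm are unknown. They depend on how often the pages disagree after cleaning, and could be zero. The illustrative loss of 2.5 to 15 men per arm (25 − 22.5 at the smallest, 50 − 35 at the largest) rests entirely on assumed values of p and m.

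The conclusion assumes that 'and' joins two conditions. A looser reading, in which the AE page alone fills the table, is possible but is not the plain sense of the sentence. Whether the overall-summary line, the listing and the narratives are affected depends on whether they use the same rule, which the SAP does not say. The correction is worth making because it is cheap and shows any discordance openly.

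**What to change.** In SAP 6.1:

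1. Tabulate and list every treatment-emergent AE with action taken 'Drug withdrawn', whatever the disposition reason, by SOC, preferred term and grade.
2. In the overall summary, report the disposition-page count (reason 'Adverse Event') beside the AE-page count, and state which source each line uses. Use one form name in SAP 4.2 and 6.1, or explain the difference.
3. Reconcile the two pages before database lock.
4. List by arm the subjects on whom the pages still differ, in either direction, with the disposition reason shown so that progression-driven stops are visible.

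The cost is SAP wording, one extra derivation and one listing, plus the reconciliation check. No clinical procedure changes. The downside is that the AE-page count may include some stops driven by disease sequelae, so the reported rate may be slightly higher; the disposition count beside it and the listing let the reader judge.

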## 6.2. Clinical Laboratory Tests

Only data collected by the central laboratory will be summarized. Local laboratory data collected for the purposes of planning treatment administration, dose modification, or monitoring adverse events, will not be summarized but will be displayed in the lab listings if needed.

Normal ranges will be used to identify values that are outside the normal ranges and abnormal laboratory results will be graded according to the NCI-CTCAE Version 4.03.

Descriptive statistics will be provided for each test result and for the change from baseline by visit.

A shift summary of baseline grade by maximum post baseline NCI-CTCAE toxicity grade will be presented, as appropriate for selected parameters. For each laboratory parameter, the baseline laboratory value will be defined as the last laboratory value collected on or prior to the date of the first dose of study drug. A listing of subjects who develop toxicities of Grade  $\geq 3$  will be provided for each lab type.

Liver function test data will be summarized based on eDISH and Hy's Law criteria. Listings will be provided for subjects who meet the eDISH criteria and Hy's Law criteria, respectively.

## 6.3. Vital Signs

Each vital sign (temperature, blood pressure (systolic and diastolic), respiration rate, and heart rate) and change from baseline for blood pressure will be summarized and presented by treatment group and study visit. Subjects with clinically significant abnormalities in vital signs as compared to baseline will be listed.

Data will be summarized and presented according to the following categories:

Parameter	Criteria for Clinically Significant Abnormality
Systolic Blood Pressure	Absolute result > 160 mmHg and increase from baseline > 20 mmHg
	Absolute result < 90 mmHg and decrease from baseline > 20 mmHg
Diastolic Blood Pressure	Absolute result > 100 mmHg and increase from baseline > 10 mmHg
	Absolute result < 50 mmHg and decrease from baseline > 10 mmHg
Weight	5 - < 10% weight loss from baseline
	10 - < 20% weight loss from baseline
	$\geq 20\%$ weight loss from baseline
	5 - < 10% weight gain from baseline
	10 - < 20% weight gain from baseline
	$\geq 20\%$ weight gain from baseline

## 6.4. Electrocardiogram

Electrocardiograms (ECGs) (12-lead) will be recorded at Screening. Abnormalities noted at screening will be included in the medical history.

## **7. PHARMACOKINETICS**

Pharmacokinetic assessment (trough PK samples) will be conducted. Pre-dose blood samples for analysis of apalutamide and the active metabolite JNJ-56142060 concentrations will be collected on Day 1 of Cycles 2, 3, 4, 5, and 6.

Descriptive statistics including mean and geometric mean values will be summarized.

Pharmacokinetic samples will be collected from at least 60 subjects who received or will receive leuprolide acetate as the GnRHa at the time of randomization. Samples will be collected on Day 1 of Cycles 1, 3, 4, 5, and 6 for analysis of leuprolide and testosterone concentrations.

Descriptive statistics of leuprolide PK data will be summarized by treatment group and dose of leuprolide acetate. Statistical analysis comparing leuprolide concentrations when administered (with placebo) alone versus in combination with apalutamide will be performed. The percentage of subjects with testosterone concentrations <50 ng/dL) will also be summarized descriptively by treatment group.

The results of these analyses will be provided in a separate report.

## **8. BIOMARKERS**

Exploratory biomarker analysis of AR anomalies and other markers previously shown to be responsible for resistance to apalutamide will be conducted and will be reported in a separate document. To determine the appropriate biomarker threshold, statistical method for evaluating treatment effect on biomarker subgroup may be utilized as appropriate.

## **9. MEDICAL RESOURCE UTILIZATION**

Data collected on medical resource utilization (MRU) will be used in the construction of economic model. The modeling analysis and reporting will be summarized in a separate report.

---

## **ATTACHMENT 1: ADDITIONAL EXPLORATORY ANALYSIS TO SUPPORT HEALTH ECONOMICS, MARKET ACCESS AND REIMBURSEMENT (HEMAR)**

### **1. DEFINITION OF SUBGROUPS**

Analysis will be performed to determine whether the treatment effect is consistent among subgroups. Analysis will be conducted for the ITT population and for the following subgroups

- For subjects that are considered high risk defined as having two of the three following high-risk factors associated with poor prognosis:
  - A Gleason score of 8 or more on a scale of 2 to 10, with higher scores indicating more aggressive disease
  - At least three bone lesions
  - The presence of measurable visceral metastasis.
- For subjects not fulfilling high risk criteria and considered low risk

### **2. TIME TO EVENT ENDPOINTS FOR SUBGROUP ANALYZES**

Kaplan- Meier estimates will be used to estimate the distribution of time to event by treatment arm based on all the ITT subjects. Data will be calculated and summarized with descriptive statistics. The following time to vent endpoints will be analysis by predefined subgroups as defined in section 1.

- rPFS
- Time to pain progression
- Time to chronic opioid use
- Time to chemotherapy
- OS
- EQ-5D and FACT P

### **3. EXPOSURE ADJUSTED INCIDENCE RATES (EAIR)**

#### **3.1. Restriction on the first event**

The analysis restricts on the occurrence of the first event per patient and ignores the existence of later (multiple) events as these cannot be assumed to occur independent of previous events (e.g.: patients suffering from infections may have in general a higher risk of having other complications and may even have a higher risk of getting other infections). The occurrence of multiple events is subject to another analysis considering the absolute number of adverse events per patient.

For these reasons the EAIR should be interpreted as 'rate until the first event occurs'. Rates estimated from several patients can be averaged on the level of a preferred term (PT), of a system organ class (SOC), or on a global level (see below).

The interpretation of EAIRs is simple and consistent on the preferred-term level only, and can be expressed as "Average number of TEAEs per preferred-term emerging per person-month of exposure".

The aforementioned considerations apply in the same way to EAIRs estimated on the global level: when EAIRs are collapsed into the global estimate (first analyses), the estimate can be interpreted as the "Average number of TEAEs emerging per person-month and PT", because estimation has been performed on a 'per PT'-basis (per average or typical PT among all PTs). Comparing EAIRs on the level of the SOC or on the global level involves data destruction because a patient's information is reduced to the first TEAE only (and possibly to a TEAE of marginal relevance among many TEAEs with higher clinical relevance).

The EAIR analysis focuses on the 'speed' by which TEAEs emerge. The analysis restricts on the first event of a patient because independence of TEAEs cannot be assumed. The necessity to restrict on the first event entails considerable data destruction when deriving SOC-specific EAIRs or the EAIR on a global level. To overcome this, the 'per PT'-analysis, which is reported in both Tables identically, is preferable.

Comparing EAIRs between the analyses outlined below on a SOC-specific or a global level demonstrates that the 'per PT'- method makes the interpretation of results more difficult. However, it can be suggested that this method provides a more robust approach when the two treatment arms are to be compared on a SOC-specific or global level. A t-Test like comparison of PT-specific estimates between the two treatment arms may provide a more robust, comprehensive and easy-to-communicate way of visualizing and comparing results.

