### 3.2. Duration of exposure: censored & non-censored

The incidence rate for a patient is derived from the duration of exposure to treatment of that patient. When averaging incidence rates a patient's duration of exposure is given either A) by the time when the event has occurred (non-censored data), or B) by the total duration of treatment in case the patient does not show the adverse event in question (censored data). Depending on whether a patient has an adverse event or not, the duration of exposure enters the denominator in its non-censored or censored form, respectively.

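### SAP Attachment 1 computes a first-occurrence rate at preferred-term level but reads it as an average number of TEAEs per person-month, which is in general a different quantity

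*SAP*

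**What the plan says.** Attachment 1 is headed as additional exploratory analysis to support health economics, market access and reimbursement.

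- **Numerator** (Section 3.1): "The analysis restricts on the occurrence of the first event per patient and ignores the existence of later (multiple) events". The reason given is that "The analysis restricts on the first event of a patient because independence of TEAEs cannot be assumed".
- **Denominator** (Section 3.2): for a man with the event, exposure is given "by the time when the event has occurred (non-censored data"). For a man without it, the whole treatment duration counts.
- **First reading** (Section 3.1): "the EAIR should be interpreted as 'rate until the first event occurs".
- **Second reading** (Section 3.1, preferred-term level, described there as the simple and consistent one): "Average number of TEAEs per preferred-term emerging per person-month of exposure". Parallel wording appears for the global level: "Average number of TEAEs emerging per person-month and PT".
- **Repeat events** (Section 3.1): "The occurrence of multiple events is subject to another analysis considering the absolute number of adverse events per patient". No method is given for that analysis in Attachment 1 or in SAP Section 6.1, which counts each subject once per term.

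Section 3.1 prefers the preferred-term analysis to the organ-class and global ones. It suggests comparing the arms on preferred-term estimates by something like a t-test.

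**The concern.** The two readings in Section 3.1 are different estimands. The estimator is first events divided by time at risk of a first event. An average number of TEAEs per person-month of exposure needs every event in the numerator and every month on drug in the denominator. The second reading is attached to the level of analysis that the SAP prefers.

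Someone who takes it literally would treat a first-occurrence rate as an event burden and the ratio of two such rates as a ratio of burdens. Exposure adjustment matters for the comparison of arms here, because the plan assumes median rPFS of 30 months on apalutamide against 20 on control, and treatment may run until progression.

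**Working it through.** The SAP gives no EAIR value, event rate or recurrence rate, so there is no planned figure to reproduce. The rates, durations and between-man variances below are assumptions.

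**Definitions.** Let λ be the mean event rate per month, T the months on drug and T₁ the time to first event.

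- SAP estimator: EAIR = P(T₁ ≤ T) / E[min(T₁, T)].
- Quantity named by the second reading: M = expected number of events by T, divided by the person-months.

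**1. Constant rate, same in every man.** P = 1 − e^(−λT) and E[min] = (1 − e^(−λT))/λ, so EAIR = λ = M. The stopped clock exactly offsets the dropped repeats, and a ratio of 2 reads as 2.00.

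**2. Repeats cluster in some men.** Section 3.1 says affected men may be at higher risk of further events. I model this with a gamma-distributed individual rate, mean λ and relative variance θ. Then P(T₁ > t) = (1 + θλt)^(−1/θ), while M is still λ.

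For T = 24 and θ = 1:

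- Control, λ = 0.05: (1 − 1/2.2) / (20 ln 2.2) = 0.5455/15.77 = 0.0346.
- Active, λ = 0.10: (1 − 1/3.4) / (10 ln 3.4) = 0.7059/12.24 = 0.0577.
- Ratio: 0.0577/0.0346 = 1.67, against a true 2.00.

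| θ | Control EAIR (true 0.05) | Active EAIR (true 0.10) | Ratio (true 2.00) |
|---|---|---|---|
| 0 | 0.0500 (100%) | 0.1000 (100%) | 2.00 |
| 0.5 | 0.0406 (81%) | 0.0727 (73%) | 1.79 |
| 1 | 0.0346 (69%) | 0.0577 (58%) | 1.67 |
| 2 | 0.0271 (54%) | 0.0415 (42%) | 1.53 |

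Over T = 12, 24 and 36, control rates of 0.01 to 0.10 and θ = 0.5 to 2, the EAIR is about 26% to 97% of the true rate. A ratio of 2 reads as 1.46 to 1.95.

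**3. One-off events, treatment continuing.** Take first-event hazards of 0.02 and 0.04 and T = 24. The EAIRs are 0.020 and 0.040, ratio 2.00. Events per person-month of exposure are (1 − e^(−0.48))/24 = 0.0159 and (1 − e^(−0.96))/24 = 0.0257, ratio 1.62. The EAIR is 26% and 56% too high as a mean count.

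**4. Early-peaking events.** Take a rate of 0.10 for 4 months and then 0.01, doubled on active, with T = 24. Mean rates are 0.6/24 = 0.025 and 1.2/24 = 0.050, ratio 2.00. The EAIRs are 0.0292 and 0.0688, ratio 2.35.

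**5. The event ends exposure.** If the drug stops at the first event, no later exposure or events are counted, so the two quantities coincide. Seizure is an example, because protocol Section 6.3 Table 1 has study drug discontinued at the first occurrence.

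**The case against.** The strongest reply is that the SAP already gives the correct reading. It says how the rate should be interpreted, adds that the analysis concerns the speed at which TEAEs emerge, and defines the stopped clock openly. First events over time at risk is a legitimate estimand. That is right, but the second reading is still wrong for the estimator, and the text does not tell the reader which to use.

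Four stronger inferences are tempting, and the documents do not support them.

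- *The EAIR always understates burden and shrinks an excess.* It does not. There is no bias in case 1, and the direction reverses in cases 3 and 4. No document gives a figure for clustering.
- *The reason for dropping repeats is a mistake.* Dependence is an acceptable motive for a first-event analysis. All events over all exposure does not need independence for its point estimate, but it is not immune to the course of treatment. Suppose each event carries an assumed 30% chance of ending drug. With 30 months of accrual, analysis near month 32, median time on drug of 20 and 30 months, a mean of 0.03 events per month on control and θ = 0.5 to 3, a true doubling then reads as about 1.9 to 1.7 per person-month. The result must be described as observed events on drug.
- *No planned analysis will ever give event burden.* The SAP announces an analysis of multiple events. It names an absolute number per patient and gives no method, so the gap is one of specification.
- *The economic model depends on this rate.* SAP Section 9 says resource-utilization data will be used to build that model. Nothing says that the EAIR feeds it.

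**Conclusion.** The mislabelling is real. At preferred-term level Attachment 1 computes a rate of first occurrence and then describes it as a mean number of events per person-month. The description is exact only under a constant, homogeneous rate or where the event ends exposure.

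Under the clustering that the SAP itself supposes, the gap is material: in the table above the control EAIR is 81% to 54% of the true rate, and a doubling reads as 1.79 to 1.53. For other event patterns the sign can change. These sizes rest on assumed rates, exposure and frailty, and they show the scale of the effect without predicting it for this trial.

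The consequence is limited. The attachment is exploratory, and the adverse event tables in SAP Section 6.1 are incidence proportions that do not use the EAIR.

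**What to change.** In SAP Attachment 1:

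1. Section 3.1: label the preferred-term EAIR *rate of first occurrence per person-month at risk*, and delete the reading as an average number of TEAEs.
2. Define the announced multiple-event analysis. For each preferred term and arm, divide all TEAEs by total person-months of exposure. Give the rate ratio and a 95% CI from a patient-level robust or bootstrap variance, or from a negative binomial model with a log-exposure offset. Describe the result as observed events per person-month on drug.

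The first-event rate stays in the plan under its correct name. The cost is a wording change and one more exploratory table from data already collected. Intervals will be wider where a few men have many repeats, which reflects the data.
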